5.2 EXCLUSION CRITERIA

- Uncontrolled ocular disease (except for MGD and dry eye disease/keratoconjunctivitis sicca) or uncontrolled systemic disease
- Patient has glaucoma, ocular hypertension, or intraocular pressure (IOP) in either eye at screening ≥ 24 mm Hg as determined by Goldman applanation tonometry (or a COVID-19 compliant device as required by local governance) or has planned insertion/removal of glaucoma filtration shunts/devices during the study
- Corneal abnormality or disorder that impacts normal spreading of the tear film (keratoconus, pterygia, scarring) or corneal integrity
- BCVA worse than 20/40 in either eye at the screening or baseline visit
- Current use of punctal plugs, anticipated insertion during the study, or a history of punctal cauterization in either eye at any time prior to the screening visit or anticipate such a procedure during the study
- Keratoconjunctivitis sicca secondary to destruction of conjunctival goblet cells as occurs with vitamin A deficiency or scarring, such as that with cicatricial pemphigoid, alkali burns, Stevens-Johnson syndrome, trachoma, or irradiation
- Keratoconjunctivitis sicca secondary to aqueous deficient DED
- Active ocular infection (bacterial, viral, or fungal) at the screening or baseline visits
- Corneal, conjunctival, or eyelid inflammation (including allergic, vernal, or giant papillary conjunctivitis and mucous membrane pemphigoid) that in the judgment of the investigator may interfere with the study results or the ability of patients to complete the treatment period
- Recent (within the past 3 months of the screening visit) ocular surgery, trauma, herpes, or recurrent inflammation
- Contact lens use anticipated during the study
- Periocular application of makeup during the study (e.g., mascara or eyeliner) that the investigator feels could interfere with the signs and symptoms of either MGD or Evaporative DED or tattooing of the lids
- Use of any type of scleral lenses or sealed compartment ocular frames within 2 months of the screening visit, or planned use during the study
- Use prohibited medications (topical, topical ophthalmic, systemic and/or injectable)

during the appropriate pre-study wash-out period and during the study.

- Unwilling to abstain from the use of systemic medications known to cause dryness for the study duration that is not used on a stable dosing regimen for at least 30 days prior to the baseline visit.
- Unwilling to abstain from the use of systemic or topical treatments for MGD or dry eye for the study duration (Including over-the-counter [OTC] artificial tears, ocular lubricants, or dietary supplements known to impact ocular surface health)
- Eyelid abnormalities that affect normal lid function in either eye other than those caused by meibomian gland dysfunction
- Diagnosis of hepatitis C infection, human immunodeficiency virus (HIV) infection, sarcoidosis, amyloidosis, active tuberculosis, or graft versus host disease
- History of anterior segment surgery or trauma that could affect corneal sensitivity (e.g., cataract surgery or any surgery involving a limbal or corneal incision) in either eye within the 12 months prior to the screening visit
- Planned anterior segment surgery (e.g., cataract surgery or any surgery involving a limbal or corneal incision) in either eye during the study period
- Meibography score at the screening visit of 4 (greater than 75% partial glands using the gestalt grading system)
- Corneal staining ≥ 3 (between 33 and 100 dots) using the Oxford Scheme
- Schirmer's tear test without anesthesia ≤ 5 mm in either eye at the baseline visit
- Known allergy or sensitivity to fluorescein, lissamine green, or the study medication or its components
- Use of medicated shampoos containing selenium (e.g., Selsun Blue, Exsel, Selsum, and Seleen) following the screening visit
- Patient is unlikely to follow study instructions or to complete all required study visits or has a condition or situation that in the investigator's opinion, may put the patient at significant risk, may confound the study results, or may interfere significantly with the patient's participation in the study
- Patient is an employee at the investigational site or is related to any member of the study staff
- Patient cannot tolerate multiple blood draws (Cohort 1 only)
- Pregnant, nursing, or females of childbearing potential and not utilizing adequate birth control measures
- Positive urine pregnancy test at the screening visit
- Participation in another clinical trial involving a therapeutic drug or device within the past 30 days
- Enrollment in a previous Stage of the current study or other Azura study using AZR-MD-001
- The patient has a screening laboratory result (e.g., hematology, serum chemistry, or urinalysis) that, in the opinion of the investigator, would make the patient unsuitable for study participation (Cohort 1 only)

5.3 LIFESTYLE CONSIDERATIONS

To be eligible for this study patient must comply with the following:

- Patients should not have LipiFlow® or other lid-heating therapy, meibomian gland probing, or therapeutic gland expression in either eye within 6 months of the screening visit or during the study.
- Patients must have discontinued (2 weeks before screening) and be willing to remain off other MGD treatments (e.g., at-home warm compress therapy, eyelid hygiene, eyelid massage, and manual lid expression) during the study.
- Patients should not have punctal plugs or plan to have punctal plugs inserted during the study.
- Patients must have discontinued (1 month before screening) and be willing to remain off antihistamines or isotretinoin during the study.
- Patients must have discontinued (3 months before screening) and be willing to remain off Anti-inflammatory treatments for DED (e.g., cyclosporine ophthalmic emulsion [Restasis® or Ikervis®] or lifitegrast ophthalmic solution [Xiidra®]).
- Patients should avoid the use of medicated shampoos containing selenium (e.g., Selsun Blue, Exsel, Selsum, and Seleen) following the screening visit.
- Patients must have discontinued (2 weeks before screening) and be willing to remain off all other prescription medications used for dry eye or MGD (e.g., antibiotics, corticosteroids, and non-steroidal anti-inflammatory drugs) during the study.
- Patients must have discontinued all other topical ophthalmic preparations (including artificial tear substitutes) other than the study drops 72 hours prior to the screening visit. If artificial tear substitutes were used within 72 hours of the screening visit the visit should be rescheduled.
- Patients must avoid periocular application of makeup during the study (e.g., mascara or eyeliner) that the investigator feels could interfere with the signs and symptoms of either MGD or Evaporative DED or tattooing of the lids

Patients should be instructed to strictly follow the visit schedule and to report any changes in condition to the investigative site personnel.

The patients should be instructed to maintain a stable dose of any concomitant medication used chronically, or any new medication initiated during the study if possible. Patients should be instructed to communicate any changes to their medication at their next study visit. Patients should also be reminded to contact the study site if they experience difficulties during their study participation.

Patients should refrain from using any ophthalmic preparations other than study treatment in order to obtain an accurate assessment of their signs and symptoms. Patients should be instructed to

communicate any changes to their ophthalmic preparations other than study treatment at their next study visit.

5.4 SCREEN FAILURES

Screen failures are defined as participants who consent to participate in the clinical trial but are not subsequently randomly assigned to the study intervention or entered in the study. A minimal set of screen failure information is required to ensure transparent reporting of screen failure participants, to meet the Consolidated Standards of Reporting Trials (CONSORT) publishing requirements and to respond to queries from regulatory authorities. Minimal information includes demography, screen failure details, eligibility criteria, and any serious adverse event (SAE).

Individuals who do not meet the criteria for participation in this trial (screen failure) because of normal variability in safety measures may be rescreened one additional time. Individuals who do not meet the criteria for participation in the trial in Cohort 1 but who may be eligible under the revised criteria for the Expansion cohort may be re-screened 1 additional time. Rescreened participants should be assigned a new screening number and the original number should not be reused.

5.5 STRATEGIES FOR RECRUITMENT AND RETENTION

Cohort 1: The total number of randomized patients for the study Cohort 1 will be approximately 60. Approximately 30 patients should have a baseline MGS score of < 6 and approximately 30 patients should have a baseline MGS score ≥ 6 and ≤ 12 . Based upon data from the LipiFlow® development program a screen failure rate of $\sim 40\%$ is expected. Thus, ~ 84 patients will need to be screened to achieve ~ 60 patients randomized to treatment.

Expansion Cohort: The total number of randomized patients, with a Total OSDI < 34 , for the Expansion Cohort will be approximately 225. Approximately 112 patients should have a baseline MGS score of < 6 and approximately 112 patients should have a baseline MGS score ≥ 6 and ≤ 12 . Based upon data from the LipiFlow® development program a screen failure rate of $\sim 40\%$ is expected. Thus, ~ 315 patients will need to be screened to achieve ~ 225 patients randomized to treatment with a Total OSDI < 34 .

Patients who have not been dosed with study drug can be reallocated from discontinued groups to increase the power in Cohort 1 groups that are continued at the discretion of the DRC.

Individual study sites may choose to advertise the study in order to facilitate patient recruitment. All advertisements will be approved by the sponsor Azura Ophthalmics, submitted to their IEC, and approved by the IEC before they are used by the site.

6 STUDY INTERVENTION

6.1 STUDY INTERVENTION(S) ADMINISTRATION

6.1.1 STUDY TREATMENT(S)/ FORMULATION(S)/ MEDICAL DEVICE COMPOSITION OR DESIGN

All concentrations of AZR-MD-001 Ophthalmic Ointment contain the drug product, AZR-MD-001 (0.1%, 0.5%, or 1.0%), and suitable excipient. The only excipient in the formulation is Petrolatum white. The AZR-MD-001 placebo to be used during the 14 day run-in period between the Screening and Baseline visits for Cohort 1 and during the treatment period for the Expansion Cohort contains only Petrolatum white. The AZR-MD-001 placebo (labelled “Vaseline”) to be used at the Baseline visit of the Expansion Cohort contains only Petrolatum white. The AZR-MD-001 vehicle to be used during the active treatment period between the Baseline and Month 3 visits for Cohort 1 contains only Petrolatum white and yellow iron oxide to match both the texture and colour of the active product. The formulations will be supplied in identical unit dose containers (see Table 6.1.1-1).

Table 6.1.1-1 Investigational Product and Packaging / Labelling Characteristics

Investigational Product			
Product name:	AZR-MD-001 (Selenium disulfide API in ointment/semi-solid Petrolatum white)	Vehicle (Cohort 1 only)	Placebo (Cohort 1& Expansion)
Formulation description:	AZR-MD-001 is an orange opaque dispersion ointment with an odour faintly of hydrogen sulfide	Ointment will match AZR-MD-001's texture and approximate its orange colour	Ointment will match AZR-MD-001's texture
Dosage form:	Ophthalmic ointment/semi-solid drug	Ophthalmic ointment/semi-solid drug	Ophthalmic ointment/semi-solid drug
Unit dose strength(s)/Dosage level(s):	Active: 0.1%/5mg (Cohort 1) 0.5%/5mg (Cohort 1 & Expansion) 1.0%/5mg(Cohort 1 & Expansion) 2.5%/5mg (Not tested, but available)	Vehicle Yellow iron oxide (colour)	Placebo Petrolatum, white
Route of Administration:	Topical	Topical	Topical
Dosing instructions:	Store between 2 – 8°C until opened. Refrigerate. Do not freeze. Discard 4 weeks (30 days) after opening. Protect from light	Store between 2 – 8°C until opened. Refrigerate. Do not freeze. Discard 4 weeks (30 days) after opening. Protect from light	Store between 2 – 8°C until opened. Refrigerate. Do not freeze. Discard 4 weeks (30 days) after opening. Protect from light
Physical description:	An orange opaque ointment packaged in a multi-use tube	An orange opaque ointment packaged in a multi-use tube	A white opaque ointment packaged in a multi-use tube
Device:	Multi-use white tube with cap	Multi-use white tube with cap	Multi-use white tube with cap
Method for individualizing dosage:	Each container/tube is placed in an individual package and appropriately labelled.	Each container/tube is placed in an individual package and appropriately labelled.	Each container/tube is placed in an individual package and appropriately labelled.

API = Active pharmaceutical ingredient

6.1.2 SELECTION OF DOSES IN THE STUDY

Azura Ophthalmics is further evaluating the safety, tolerability and effectiveness of AZR-MD-001 ointment/semi-solid drug, surfactant free, in topical ophthalmic concentrations between 0.1% and 2.5% based upon positive results from clinical study MGSS1 using a 2.5% selenium disulfide concentration, published clinical studies (see the Investigators' Brochure for more detail) demonstrating the safe and effective treatment of seborrheic blepharitis with selenium sulfide exposures up to 0.5% twice-daily, pre-clinical safety data with exaggerated dosing up to 2.5% with the clinical formulation and the maximum concentration fulfils the criteria for a low risk Schedule 2 (Pharmacy medicine) classification as specified in the Australian Poisons Standard October 2017 (Standard for the Uniform Scheduling of Medicines and Poisons (SUSMP), No. 18) (see Table 6.1.2-1).

Table 6.1.2-1: Australian Poisons Standard for Selenium

Australian Poisons Standard Dated 26th September 2017			
Schedule	Description	Topical	Oral
1	Schedule is intentionally blank.		
2	Pharmacy Medicine -Safe use may require advice from a pharmacist or licensed person.	For human topical use of 3.5% or less	For human oral use with a recommended dose of 150 micrograms or less
3	Pharmacist Only Medicine -Safe use requires advice from a pharmacist without a prescription.		
4	Prescription Only Medicine -Use should be ordered by persons permitted by State or Territory legislation to prescribe and should be available from a pharmacist on prescription.		For human oral use with a recommended dose of 300 micrograms or more
6	Poison -Substances with a moderate potential for causing harm, the extent of which can be handled through distinctive packaging and strong safety labeling.		In this schedule if it occurs with an "arsenic" (i.e., selenium arsenide)

Azura Ophthalmics believes that the use of AZR-MD-001 ointment/semi-solid drug with selenium disulfide in a concentration range between 0.1% to 2.5% is likely to safely and effectively treat MGD with or without associated evaporative dry eye disease.

6.1.3 DOSING AND ADMINISTRATION

For Cohort 1, the study medication will be self-administered by the patient (or administered by a caregiver) at the study site after all procedures have been completed for the run-in and post-randomization visits. At these visits, each patient will be asked to stay at the site for 30 minutes after study drug administration. No other dosing will be done in office as the product will be dosed in the evening only.

For the Expansion Cohort, the study medication will be self-administered by the patient at the study site after all procedures have been completed for the baseline visit only using "Vaseline". At this visit, each patient will be asked to stay at the site for 30 minutes after study drug administration. No other dosing will be done in office as the product will be dosed in the evening only.

Patients (or a caregiver) will apply a dose of approximately 5 mg using a dosing aid supplied by Azura Ophthalmics. Patients will then use their washed index finger (Cohort 1 and Expansion Cohort) or an applicator (Cohort 1 only) to apply the drug to the tarsus of the lower lid of both

eyes in the evening just before bedtime. The patient will then blink several times to transfer a portion of the drug from the lower eyelid to the upper eyelid (see the Dosing Instruction Sheet for more detail).

During the double-masked treatment period, each patient (or caregiver) must apply 1 application of the assigned treatment in the evening to the tarsus of the lower lid of both eyes.

Multi-dose tubes of the masked study medication are each to be used for only 30 days to both eyes. The patient should be instructed to place the used tube in the used tube bag after 30 days and should return used and unused tubes at the next study visit to the study site.

6.2 PREPARATION/HANDLING/STORAGE/ACCOUNTABILITY

6.2.1 ACQUISITION AND ACCOUNTABILITY

Whilst patients are dosed at site (i.e., Cohort 1 all visits, and practice dose at the baseline visit only of the Expansion Cohort), they will administer their study treatment under medical supervision. The date and time of each dose administered in the clinic will be recorded in the source documents. The dose of study treatment and study subject identification will be confirmed at the time of dosing by a member of the study site staff.

Patients will be instructed on proper instillation and storage of study drug at the end of each visit, and will be given written instructions and may also watch an instructional video at the baseline visit. The used study drug tubes will be collected at each visit from baseline up to and including study exit (along with any unused tubes) to assess dosing and symptom assessment compliance. Dosing compliance will be based off of the used and unused tube count. If the subject is less than 80% or more than 125% compliant with dosing based on the expected number of used tubes, then the subject will be deemed non-compliant and a deviation should be recorded.

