1.2 SCHEMA

Study Design: *Structure:* Multicenter, double-masked, vehicle-controlled, randomized, parallel group study carried out in 2 sequential cohorts - Cohort 1: sequential rising concentrations of AZR-MD-001 ointment/semi-solid drug (i.e., 0.1%, 0.5%, or 1.0%) and AZR-MD-001 vehicle dosed twice-weekly and/or once daily in the evening; Expansion Cohort: parallel doses of two concentrations of AZR-MD-001 ointment/semi-solid drug (i.e., 0.5% and 1.0%) and AZR-MD-001 placebo dosed twice-weekly in the evening.

Cohort 1:

For Cohort 1, 2 sequential groups of 10 patients each will be followed by 2 sequential groups of 20 patients each. All patients will be diagnosed with MGD and signs and symptoms of Evaporative DED and they will be randomly assigned in a 4:1 ratio to receive either a single concentration of AZR-MD-001 ointment/semi-solid drug (i.e., 0.1% for Group 1, 0.5% for Group 2, 1.0% for Group 3, and a 0.5% for Group 4) or AZR-MD-001 vehicle twice weekly for 1 month. The patients in either the active or vehicle groups will further be assigned in a 1:1 ratio to 1 of 2 treatment regimens at the baseline visit: 1) they will receive treatment twice weekly for their entire 3 month treatment period; or 2) they will receive treatment twice weekly for the first month of their treatment period and will then receive treatment once every evening for months 1 to 3 of their treatment period. At the day 14 visit for the 10th patient in groups 1 and 3 and at month 1.5 for group 2, an unmasked Data Review Committee (DRC) will review all the tolerability and safety data for the patients and recommend a starting dose for the next group of patients (i.e., the DRC can elect not to escalate the dose concentration and can instead repeat a dose that has already been tested). At the month 1 visit the investigator will determine, by patient, if the treatment was well tolerated. If the regimen was well tolerated, the patients will continue their assigned dosing regimen (twice weekly dosing) or escalate to once daily dosing, based on their treatment regimen assigned at the baseline visit. If the investigator does not feel it is safe to escalate dosing and it is safe to continue dosing with the current regimen for a particular patient, that patient will be instructed to continue on their current regimen irrespective of treatment assignment.

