6.2.4 PREPARATION

Patients should let the study tube equilibrate at room temperature below 25°C for up to 15 minutes before dosing. Patients will use the study medication directly from the dose container in accordance with the protocol and should return the dose container to refrigeration between 2 – 8°C following successful dosing. For the next day of dosing, this process should be repeated. This in use pattern should continue for 30 days at which time the dose container should be used for a final day of dosing and then discarded.

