10.1. Extent of Exposure and Compliance

During the Baseline visit, the patient will be dispensed Vaseline, which will be administered while on site and the prospective patient will be observed by the physician or a designee. Eligible patients will also be dispensed randomized study medication (AZR-MD-001 or placebo), which will be administered twice weekly at home. Patients are expected to apply the first application of randomized study medication on the same date, in the evening.

Application, dispensation, and return of randomized study treatment will be listed chronologically by patient and visit. A separate listing of Physician Observation of Drug Application, for observation of Vaseline applied during the Baseline visit, will be provided.

Compliance for randomized study treatment, in the form of numbers of doses administered and missed, is collected in 6-week intervals. Approximately 12 doses are expected to be administered during each of those 6-week periods, but slightly more or less may be expected depending on actual visit dates and visit windows. The expected number of doses for a given period is calculated as $2 \times (\text{end date} - \text{start date} + 1) / 7$, rounded to the nearest whole number. Compliance is then calculated as $100 \times (\text{number of doses taken}) / (\text{number of expected doses})$.

Overall compliance for the 3 month study period will be based on the expected numbers of doses calculated as $2 \times ([\text{Month 3 visit date or date of discontinuation}] - [\text{date of first dose}] + 1) / 7$, for the 3 month study period, and $2 \times ([\text{Month 6 visit date or date of discontinuation}] - [\text{date of first dose}] + 1) / 7$, for the 6 month period including follow-up. The number of patients with compliance <80%, 80%-120%, and >120% will be tabulated.

For the safety follow-up period, if the final study drug is returned after the Month 6 visit (based on the visit date as compared to the final study drug return date), compliance will be calculated based on the Month 6 visit date. If dates of dispensation or return are not recorded on the eCRF (e.g., visit restrictions were in place and study treatment was mailed to patients), compliance calculations will be based on the assumption that 12 doses should have been administered.

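### The protocol's numeric compliance deviation counts tubes retired every 30 days, so it tracks elapsed time rather than doses and can disagree with the SAP's dose-based compliance table.

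*Protocol*

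**What the plan says.** Protocol 6.2.1 defines the measure: "Dosing compliance will be based off of the used and unused tube count". The numeric limits follow: "If the subject is less than 80% or more than 125% compliant with dosing based on the expected number of used tubes", the patient is non-compliant and a deviation is recorded. The expected number of used tubes, and the period over which the percentage is judged, are not given.

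Protocol 6.1.3 fixes the life of a tube: "Multi-dose tubes of the masked study medication are each to be used for only 30 days to both eyes". It also says when a tube becomes a used one: "The patient should be instructed to place the used tube in the used tube bag after 30 days". Protocol 6.2.4 agrees: "This in use pattern should continue for 30 days", after which the container is discarded. None of these sections mentions weighing, residual content or a dosing diary.

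The Expansion Cohort regimen is twice weekly in all arms; for the control arm, Protocol 1.2 has "AZR-MD-001 placebo dosed twice-weekly in the evening". In Cohort 1, one of the two regimens moved to every-evening dosing after Month 1, under the same 30-day tube rule.

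The SAP measures something else. Section 10.1: "Compliance for randomized study treatment, in the form of numbers of doses administered and missed, is collected in 6-week intervals". Expected doses are two per week, about 12 per six-week interval, and "The number of patients with compliance <80%, 80%-120%, and >120% will be tabulated". SAP section 12, which lists changes from the protocol's analyses, does not mention compliance.

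**The concern.** A used-tube count is a measure of dosing only if using more drug consumes more tubes. Here a tube is retired by date, so one tube is used per 30 days whether it was opened once or every night. The limits of 80% and 125% look like a check on under- and over-dosing, but departures in dosing frequency do not move the quantity they are applied to.

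Two things are at stake. The first is whether the site's numeric flag fires when a twice-weekly patient doses much more or much less often. The second is consistency. A patient could fall in the SAP's top or bottom compliance band with no compliance deviation under 6.2.1, or be fully compliant by doses and carry one because a tube count was off.

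**Working it through.** **Inputs**
- Tube life: 30 days (Protocol 6.1.3, 6.2.4).
- Month = 28 days (Protocol Table 1 footnote), so Month 1.5 = 42 days, Month 3 = 84 and Month 6 = 168.
- Expected doses for a period = 2 × (end − start + 1)/7, rounded (SAP 10.1).
- Expected tubes: not stated. Assumed here to be days/30 rounded up, counting every opened tube as used.

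**Step 1: reproduce the SAP's figure.** For 42 days, 2 × 43/7 = 12.29, which rounds to 12 and matches the SAP's approximate figure. For 84 days, 2 × 85/7 = 24.29, which rounds to 24.

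**Step 2: what one tube represents.** Over 30 days, twice-weekly dosing is 30 × 2/7 = 8.6 applications and nightly dosing is 30. Each counts as one used tube.

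**Step 3: the two measures over 84 days.** Expected tubes: 84/30 = 2.8, rounded up to 3.

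| Pattern | Doses | Dose compliance (of 24) | Used tubes | Tube compliance |
|---|---|---|---|---|
| Nightly | 84 | 350% | 3 | 3/3 = 100% |
| Once weekly | 12 | 50% | 3 | 3/3 = 100% |
| One use per tube | 3 | 12.5% | 3 | 3/3 = 100% |

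By doses, all three lie outside both 80%–125% and 80%–120%. By tubes, none is flagged.

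**Step 4: does the assumed tube count matter?** Suppose instead that two tubes are started in each six-week interval, so four through Month 3. Every pattern then gives 4/4 = 100%, and one use per tube is 4/24 = 16.7% by doses. Whatever tube number is expected, patterns that retire tubes on schedule give the same count.

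**Step 5: sensitivity to one tube.** The effect of a count that is one tube off does depend on the period:
- 42 days, 2 tubes: 1/2 = 50% or 3/2 = 150%; both flagged.
- 84 days, 3 tubes: 2/3 = 66.7% or 4/3 = 133.3%; both flagged.
- 84 days, 4 tubes: 3/4 = 75%, flagged; 5/4 = 125%, not above the limit.
- 168 days, 6 tubes: 5/6 = 83.3% or 7/6 = 116.7%; neither flagged.

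Over the shorter periods a single-tube discrepancy can trigger the flag while the misdosing in Step 3 does not.

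**The case against.** The case on the other side is substantial as to consequences.

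- **Other routes to a deviation.** Protocol 9.3 treats any noncompliance with the protocol as a deviation, so nightly dosing in the Expansion Cohort is one regardless of tubes. Doses taken are recorded on a compliance eCRF (SAP 5.2.1), and SAP section 7 has deviations identified and graded by the investigator and a team, with a further review before the freeze. A reader might infer that gross overuse would go undetected. The documents do not support that; the failure is confined to the numeric rule in 6.2.1.
- **Reported compliance is sound.** SAP Tables 17 and 17.1 use doses and would show the patterns in Step 3.
- **Per-Protocol sets.** A reader might infer that these sets will keep badly misdosed patients or lose well-dosed ones. Only Grade 4 or 5 deviations exclude a patient, and the grade of a compliance deviation sits in a separate definitions document cited in SAP section 7. The inference cannot be checked here.
- **A mislaid tube.** A reader might infer that losing one tube makes a fully dosed patient non-compliant. SAP 2.5 records unreturned tubes separately and neither document says how they count. Step 5 also shows that the result depends on the period.
- **Different limits.** 125% and 120% apply to different measures, one as a site trigger and one as a display band, so the difference alone is not a contradiction.
- **Unopened tubes.** A patient who stops and returns tubes unopened is caught by the tube count.

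All of this stands, and it narrows the point. None of it makes the tube count respond to dosing frequency. Nor does the mention of unit-dose containers in Protocol 6.1.1 help: Table 6.1.1-1 and section 6.1.3 describe multi-use tubes, and a container count would follow doses only with single-dose packs.

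**Conclusion.** The point holds for the rule in Protocol 6.2.1. Under it, dosing at 350%, 50% and 12.5% of the expected number all read 100% over 84 days. This rests on two assumptions: each tube is opened and retired on schedule, and, for nightly use, one tube holds 30 nightly applications. No fill weight is given for the second, but Cohort 1's nightly regimen under the same 30-day rule suggests it.

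The site flag and the SAP table can therefore disagree for the same patient, and SAP section 12 does not record that the measure differs. The primary analysis is on the ITT Set (SAP 8.1), which includes all randomized patients whatever their compliance, so it is unaffected. An effect on the Per-Protocol sets is possible but not shown. Severity is minor to moderate.

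**What to change.** In Protocol 6.2.1, base the compliance deviation on doses taken divided by doses expected, from the compliance eCRF and with the SAP 10.1 formula. State the period over which it is judged. Keep the tube count for drug accountability and as a cross-check, and state how unreturned tubes are treated. Reconcile the limits (80%–125% in the protocol, 80%–120% in the SAP), or explain why they differ. If the protocol is not amended, list the change of measure in SAP section 12 and say which measure generates the deviation that is graded under SAP section 7.

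The cost is wording, since the dose counts are already collected. The drawback is that they appear to be patient-reported, with no diary described, which is a reason to retain the tube count as a physical check.
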